## 7.2. Participant Discontinuation/Withdrawal from the Study

## 7.2.1. Participant Withdrawal

A participant may withdraw from the study:

- at any time at his/her own request
- at the request of his/her designee (for example, parents or legal guardian)
- at the discretion of the investigator for safety, behavioural, compliance, or administrative reasons
- if enrolment in any other clinical study involving an investigational product or enrolment in any other type of medical research judged not to be scientifically or medically compatible with this study
- if the participant needs to be stopped for medical, safety, regulatory, or other reasons consistent with applicable laws and regulations, or
- if the participant, for any reason, requires treatment with another therapeutic agent that has been demonstrated to be effective for treatment of the study indication, discontinuation from the study occurs prior to introduction of the new agent.

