1.2. Study Design

1.2.1. Overall Design

Study F3Z-MC-IORW (IORW) is a multicenter, open-label, controlled, single-arm pragmatic outpatient study in participants with T1D or T2D that comprises of 2 study periods, including:

- a 6-week run-in period (Study Period 1) when insulin timing and dosage data

 CCl is masked to the participant using the Glooko® Research Mobile Application (RMA) and is unmasked to the healthcare professional (HCP) using the Glooko HCP platform, and
- a 12-week intervention period (Study Period 2) when insulin timing and dosage data

[figure not shown]
 CCI is unmasked to the participant using the Glooko RMA and the HCP using the Glooko HCP platform.

Study IORW will be carried out in France and will include up to 10 clinical study sites. The study is expected to last approximately 16 months, with each participant duration of approximately 18 weeks. Approximately 50 participants will be enrolled in the study. Best efforts will be made to enroll a participant ratio of 4:1 for participants with T1D to participants with T2D.

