2.1. Multiplicity Adjustment

A p-value of \leq 0.05 will be considered statistically significant. No adjustments for multiplicity will take place.

3. Analysis Sets

For the purposes of analysis, the following analysis sets are defined:

Participant Analysis Set	Description			
Main Analysis Set	All continuous glucose monitoring (CGM) data should be included in the final analysis, but the proportion of participants who met the minimum 70% data-obtainment requirement during 14 days should be reported as part of the data completeness. Participants with ≥70% of CGM data present for a particular day will be considered complete for the day or valid CGM day. Similarly daytime and nighttime periods will be checked separately for valid CGM period. Following the guidelines of the Advanced Technologies and Treatments for Diabetes (ATTD) consensus on CGM use, only participants with at least 10 days' worth of valid CGM data out of the last 14 days (Weeks 5 and 6) in the masked application period will be considered for the main analysis set (Danne et al. 2017; Battelino et al. 2023).			
	Among these participants, only participants that satisfy the below criteria for the unmasked application period will be considered as evaluable participants and included in the main analysis set:			
	 participants with at least 20 of 28 days' worth of CGM data (Weeks 15 to 18), or participants discontinuing early that have at least 20 days' worth of CGM data in the whole unmasked application period (Weeks 7 to 18). 			
	Efficacy analyses will be carried out on the main analysis set. To allow for this clinical trial to be generalizable to the wider population and to prevent the chance of analyzing a biased set of "only adherent" participants, efficacy analyses will be repeated on the sensitivity analysis set.			
Sensitivity Analysis Set	The sensitivity analysis set includes all participants in the main analysis set, plus participants with at least 10 days' worth of CGM data in the whole masked application period (Weeks 1 to 6), and all participants with at least 20 days' worth of CGM data in the whole unmasked application period (Weeks 7 to 18).			
Safety Analysis Set	Safety analyses will be carried out on the Safety Population, which consists of all participants with at least 1 measurement in the masked application period and/or unmasked application period.			

4. Statistical Analyses

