4.6. Other Safety Analyses

Analyses of AEs will be descriptive and include all data collected during the treatment period. All AEs will be coded using the standardized Medical Dictionary for Regulatory Activities (MedDRA) central coding dictionary, version 24.1 or greater. Safety analysis and all analyses of adverse events will be carried out on the safety population.

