4.6.4. Hypoglycemic Events

The number of hypoglycemic events (CGM levels below the threshold for at least 15 minutes) will be summarized by study period in a table (Danne 2017). A data listing will also be generated. The number of Level 1 (\leq 70 mg/dL) and Level 2 (\leq 54 mg/dL) sensor detected hypoglycemic events will be summarized in a table, as well as participant-reported hypoglycemia if available.

Level 3 hypoglycemic events, which are considered as SAEs, will also be summarized and listed.

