4.9. Interim Analyses

No Interim Analysis will be performed.

5. Sample Size Determination

This clinical study aims to enroll approximately 50 participants (in other words, with signed informed consent and meeting all eligibility criteria) in sites across France. This sample size provides ≥80% power to detect a mean difference of daily MBD of 0.323 between the unmasked and masked RMA periods.

The sample size also assumes:

- a conservative correlation estimate of 0.2 between the unmasked and masked RMA periods
- an SD of 0.419 for the mean difference, and
- a 2-sided alpha of <0.05 (Adolfsson et al. 2020).

The estimated mean difference of 0.323 daily MBD is equivalent to a clinically relevant improvement of approximately 2.3 fewer MBD per week in the unmasked RMA period compared to the masked RMA period (also approximately 11% improvement).

A sample size of approximately 50 participants will be sufficient to allow:

- at least 24 participants will complete the study with analyzable data
- scope for increased variability (up to SD of 0.5)
- for non-analyzable participants due to technical problems, and
- 35% dropout rate is assumed based on previous study results (Adolfsson et al. 2020; Gomez-Peralta et al. 2023) and the impact of missing CGM data which will reduce the number of evaluable participants.

Participants who are entered but who do not proceed to the unmasked stage will be discontinued from the final efficacy analysis and may be replaced to ensure that enough participants complete the study. Best effort will be made to recruit an approximate ratio of 4:1 for T1D and T2D (approximately 40 participants with T1D and 10 participants with T2D) in this clinical study.

Withdrawals will be monitored to ensure there are enough participants with T2D enrolled.

6. Supporting Documentation

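### The by-period table of sensor hypoglycaemia counts compares 6 weeks with 12 weeks in partly different people, so it cannot be read as before versus after unmasking

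*SAP*

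**What the plan says.** SAP 4.6.4 (Hypoglycemic Events): "The number of hypoglycemic events (CGM levels below the threshold for at least 15 minutes) will be summarized by study period". It also plans a data listing and a table of the number of Level 1 and Level 2 sensor-detected events. It names no rate, no denominator of CGM time, no within-participant change and no test.

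The population comes from SAP 4.6: "Safety analysis and all analyses of adverse events will be carried out on the safety population". SAP Section 3 (Safety Analysis Set) defines it as "all participants with at least 1 measurement in the masked application period and/or unmasked application period". Data in both periods are not required.

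SAP 1.2.1 sets Period 1 (masked) at 6 weeks and Period 2 (unmasked) at 12 weeks.

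Three passages bear on who contributes to each period:
- Protocol 7.1: a participant who permanently stops the intervention is not kept in the study for evaluation.
- SAP Section 5: "Participants who are entered but who do not proceed to the unmasked stage will be discontinued from the final efficacy analysis and may be replaced". This removes them from efficacy only, so their Period 1 events stay in the safety table.
- Protocol 7.2.1 allows withdrawal "at the discretion of the investigator for safety, behavioural, compliance, or administrative reasons".

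Protocol 4.4.2 and 6.3 rest the single-arm design on each participant serving as their own control.

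**The concern.** A safety table with one column for the masked period and one for the unmasked period will be read as before versus after, even without a test. Here the columns differ in two ways that have nothing to do with unmasking.

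First, Period 2 is nominally twice as long, and the planned quantity is a number of events. Second, the columns hold partly different people: Period 1 includes everyone who later leaves, while Period 2 loses them wholly (exit before Visit 3) or in part (exit during Period 2). The own-control logic that protects the efficacy endpoints is therefore lost for hypoglycaemia. The protocol names that risk itself: Section 6.5 links excess insulin to hypoglycaemia, and Section 2.4.2 lists overdose through the platform as a potential risk.

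At stake is whether the trial can say if sensor hypoglycaemia rose, fell or stayed the same after unmasking. From this table it could not, in either direction.

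**Working it through.** The documents give no hypoglycaemia rate or expected count, so there is no stated figure to reproduce. The check asks what the table would show if nothing changed within any participant.

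**Inputs**
- Period lengths: 6 and 12 weeks (SAP 1.2.1).
- Dropout: SAP Section 5 assumes 35%, in a bullet that also covers missing CGM data. Protocol 7.2.2 expects discontinuation to be uncommon. So 35% is an upper bound for people leaving; 10% and 20% are assumed lower values.
- d = share leaving before Period 2, each assumed to contribute all of Period 1.
- r = leavers' weekly event rate divided by stayers' (assumed; stayers' rate set to 1).

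**Step 1: length alone.** With no dropout and no change, the count ratio is 12/6 = 2.

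**Step 2: counts with dropout.**
- Total count ratio (P2/P1) = 12(1−d) / {6[(1−d)+d·r]} = 2(1−d)/[(1−d)+d·r]
- Mean count per contributing participant = 2/[(1−d)+d·r]

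| d | r | Total count ratio | Mean count ratio |
|---|---|---|---|
| 10% | 1.5 | 1.80/1.05 = 1.71 | 2/1.05 = 1.90 |
| 20% | 2 | 1.60/1.20 = 1.33 | 2/1.20 = 1.67 |
| 35% | 2 | 1.30/1.35 = 0.96 | 2/1.35 = 1.48 |
| 35% | 3 | 1.30/1.70 = 0.76 | 2/1.70 = 1.18 |

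The total falls only if r > (1−d)/d, that is 9.0, 4.0 and 1.86 at d = 10%, 20% and 35%. The mean falls only if r > (1+d)/d, that is 11.0, 6.0 and 3.86. In most scenarios raw counts make Period 2 look worse.

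**Step 3: rates.** Rate ratio (P2/P1) = 1/[(1−d)+d·r]

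| d | r = 0.5 | r = 1 | r = 1.5 | r = 2 | r = 3 |
|---|---|---|---|---|---|
| 10% | 1.05 | 1.00 | 0.95 | 0.91 | 0.83 |
| 20% | 1.11 | 1.00 | 0.91 | 0.83 | 0.71 |
| 35% | 1.21 | 1.00 | 0.85 | 0.74 | 0.59 |

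Dividing by exposure removes the doubling but leaves a composition effect of either sign. At d = 20%, r = 2, a true 20% rise among stayers gives 1.2/1.2 = 1.00 on the rate scale.

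**Step 4: timing of exit.**
- If 35% leave midway through Period 2 at r = 2, the Period 2 rate is (0.65×12 + 0.35×6×2)/(0.65×12 + 0.35×6) = 12.0/9.9 = 1.21. The Period 1 rate is 1.35, so the ratio is 0.90.
- If 20% leave midway through Period 1 at r = 2, the pooled Period 1 rate is (0.8×6 + 0.2×3×2)/(0.8×6 + 0.2×3) = 6.0/5.4 = 1.11, so the ratio is again 0.90.

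**Step 5: same people, rate scale.** Restricted to participants with data in both periods and expressed per unit of CGM time, each participant's ratio is 1.00 in every no-change scenario above.

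**The case against.** **The table is descriptive.** The SAP plans a summary, with no test and no stated conclusion. That is correct, and it limits the point to reporting. It does not make the columns comparable.

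**Low glucose is already analysed in the same people.** Time below range (<70 and <54 mg/dL) has repeated-measures model code in SAP 4.4.1.1.4, in the main analysis set, which requires CGM data in both periods. SAP 4.1 repeats efficacy analyses on the sensitivity set. This is a real partial check. However, it measures percent of time rather than events, depends on CGM completeness rules, and by default uses Weeks 5–6 and 15–18. It therefore says little about Weeks 7–14, the weeks after the Visit 3 data review.

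**Leavers can be seen elsewhere.** Disposition by period and reason (SAP 4.2), listings of adverse events leading to discontinuation (4.6.1), narratives (4.6.2) and the event listing (4.6.4) all help. None gives a paired event rate or the leavers' Period 1 rate.

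**A paired figure has its own selection.** It rests on people who stayed, and over the whole of Period 1 it includes the four settling-in weeks that the plan keeps out of baseline. Both limits stand, so the paired figure should sit beside the full table and not replace it.

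**A reader might infer that selective dropout will make unmasking look safer.** The documents do not support that. The planned quantity is a count over 6 versus 12 weeks, which mostly pushes the other way. Nothing shows that leavers have more hypoglycaemia: the withdrawal clause also covers behavioural, compliance and administrative reasons, and people who miss boluses could have fewer events. Nor can all of the 35% be treated as leaving before Period 2, or the Period 2 column as completers only.

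**Conclusion.** The point holds as a reporting defect of undetermined direction. As planned, the by-period counts mix unequal exposure with changing membership and cannot support a statement about change in hypoglycaemia after unmasking.

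The exposure part follows from the period lengths alone: a factor of 2 with no change and no dropout. The composition part is conditional. It depends on an assumed share of leavers, their relative rate and when they leave, none of which the documents give. It vanishes if leavers and stayers have the same rate, and it may be small if discontinuation is as uncommon as Protocol 7.2.2 expects. The rate ratios of 0.83, 0.74 and 1.21 illustrate the possible size and sign; they are not predictions.

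**What to change.** In SAP 4.6.4:
1. Keep the all-participant table by study period, but report Level 1 and Level 2 events per participant-week of CGM data, with the CGM time shown.
2. Add, for participants with CGM data in both periods, the within-participant difference in rate (Period 2 minus Period 1) with a 95% CI, for each level. State in a footnote which weeks are used.
3. Show the Period 1 rate separately for participants who did not enter Period 2.
4. State that any comment on change in hypoglycaemia will be read from the paired figure alongside the full table and the leavers' rate, not from the unpaired counts.

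The cost is one extra table from data already being derived. The paired figure rests on fewer, retained participants, which is why the other two displays stay next to it.

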4.7. Vital Signs, Physical Findings, and Other Observations Related to Safety

4.7.1. Vital Signs and Physical Characteristics

Baseline vital signs (height, weight, and BMI calculated from height and weight) will be summarized in a table in the safety population.

Height, weight, and BMI changes from baseline at Visit 3 and Visit 7 will also be summarized.

A listing will be generated of any conditions recorded during the baseline physical examination.

4.8. Other Analyses

4.8.1. Other Sensitivity Analyses

Other sensitivity analyses that will be explored using descriptive analysis include the number of:

- weeks used in the analysis for the masked application period,
- days with CGM data in the unmasked application period, and
- participants that have dropped out during the unmasked application period.

4.8.2. Subgroup Analyses

Subgroup analysis will be performed on all participants for primary and secondary endpoints by the following factors:

- age group, and
- diagnosis (T1D or T2D).

Only summary statistics will be performed for all subgroups listed above.

4.9. Interim Analyses

No Interim Analysis will be performed.

5. Sample Size Determination

This clinical study aims to enroll approximately 50 participants (in other words, with signed informed consent and meeting all eligibility criteria) in sites across France. This sample size provides ≥80% power to detect a mean difference of daily MBD of 0.323 between the unmasked and masked RMA periods.

The sample size also assumes:

- a conservative correlation estimate of 0.2 between the unmasked and masked RMA periods
- an SD of 0.419 for the mean difference, and
- a 2-sided alpha of <0.05 (Adolfsson et al. 2020).

The estimated mean difference of 0.323 daily MBD is equivalent to a clinically relevant improvement of approximately 2.3 fewer MBD per week in the unmasked RMA period compared to the masked RMA period (also approximately 11% improvement).

A sample size of approximately 50 participants will be sufficient to allow:

- at least 24 participants will complete the study with analyzable data
- scope for increased variability (up to SD of 0.5)
- for non-analyzable participants due to technical problems, and
- 35% dropout rate is assumed based on previous study results (Adolfsson et al. 2020; Gomez-Peralta et al. 2023) and the impact of missing CGM data which will reduce the number of evaluable participants.

Participants who are entered but who do not proceed to the unmasked stage will be discontinued from the final efficacy analysis and may be replaced to ensure that enough participants complete the study. Best effort will be made to recruit an approximate ratio of 4:1 for T1D and T2D (approximately 40 participants with T1D and 10 participants with T2D) in this clinical study.

Withdrawals will be monitored to ensure there are enough participants with T2D enrolled.

6. Supporting Documentation

6.1. Appendix 1: Demographic and Baseline Characteristics

Demographics and other baseline characteristics will be analyzed on the safety population, unless otherwise specified in the subsections.

6.1.1. Demographics

Demographics and baseline characteristics will be presented in a table including age (in years), diabetes type, diabetes duration, gender, ethnicity, and baseline BMI and HbA1c. This table will be completed in the main analysis set, the sensitivity analysis set, and safety population. T1D and T2D participant's characteristics will be presented separately.

6.1.2. Concomitant Medications

Concomitant medications will be presented in a listing in the safety population. Additionally, a summary of glucose lowering concomitant therapy/insulin regimen will be completed in the safety population as well as specifically for participants with T2D.

6.1.3. Baseline Medical History

Medical history will be presented in a table in the safety population. A data listing will also be generated.

6.2. Appendix 2: Timing of Assessments and Events for Analysis

Study Day 1 is the date in which the participants start Visit 1. Study days will be calculated as follows:

 $Pre\ first\ usage,\ study\ days = event\ date - Visit\ 1\ date$

On the day of or post data upload, study days = event date -Visit 1 date +1

The initial 4 weeks of the study will be used to allow participants to reach a routine before the baseline data assessment. Therefore, unless otherwise stated, data collected from the last 2 weeks of the masked period (Study Period 1, Weeks 5 and 6) will be used as baseline. Data from the last 4 weeks of the unmasked period (Study Period 2, Weeks 15 to 18) will be used for endpoint, in other words, 2 weeks prior to Visit 3 (face-to-face) and 4 weeks prior to Visit 7 (face-to-face) will be used. Data from these specified timepoints will be used to assess the primary and secondary objectives.

6.3. Appendix 3: Exposure to the GLOOKO Research Mobile Application

Amount of useable data from the CGM device and pen will be summarized for the main analysis set and presented in a table.

6.4. Appendix 4: Clinical Trial Registry Analyses

Additional analyses will be performed for the purpose of fulfilling the Clinical Trial Registry (CTR) requirements.

Analyses provided for the CTR requirements will include the following:

- summary of AEs, provided as a dataset which will be converted to an XML file, and
- SAEs and 'Other' non-SAEs summarized by treatment group and MedDRA PT.

An AE is considered 'Serious' whether or not it occurred after study Day 1.

An AE is considered in the 'Other' category if it occurred after study Day 1 and is not serious. For each SAE and 'Other' AE, for each term, the following are provided:

- the number of participants at risk of an event
- the number of participants who experienced each event term, and
- the number of events experienced.

For each SAE, these additional terms are provided for EudraCT:

- the total number of occurrences causally related to treatment
- the total number of deaths, and
- the total number of deaths causally related to treatment.

Consistent with www.ClinicalTrials.gov requirements, 'Other' AEs that occur in fewer than 5% of participants in every treatment group may be excluded if a 5% threshold is chosen. Allowable thresholds include 0% (all events), 1%, 2%, 3%, 4%, and 5%.

AE reporting is consistent with other document disclosures for example, the CSR, manuscripts, and so forth.

A demographic table including the following age ranges is required by EudraCT:

- in utero
- preterm newborn infants (gestational age <37 weeks)
- newborns (0–27 days)
- infants and toddlers (28 days–23 months)
- children (2–11 years)
- adolescents (12–17 years)
- adults (18–64 years)
- 65–84 years, and
- 85 years and over.

This study will include adults (18–64 years).

